#### 8.8 SAFETY ANALYSES

Safety analysis will be performed among patients who received at least a partial dose of study drug. If a patient experiences the same adverse event more than once, then the patient will be counted only once for that adverse event for frequency counts. Similarly, if a patient has more than one adverse event in a single SOC, then the patient will be counted only once for that SOC.

If a patient has taken the same concomitant medication (as coded to World Health Organization (WHO) PT) more than once, then the patient will be counted only once for that concomitant medication.

#### **8.8.1** Adverse Events

The AE terms will be coded by system organ class (SOC) and preferred term (PT) using the Medical Dictionary for Regulatory Activities (MedDRATM) Dictionary (Version 17.1 or later). AEs will also be presented by the Common Terminology Criteria for Adverse Events (CTCAE) version 5.0 (National Cancer Institute) NCI (Version 5.0) from Grade 1-Grade 5 of mild, moderate, severe, Life-threatening and death and by relationship to study drug. AEs will be presented by severity only when the CTC grade is not collected.

The Following Tables will be Provided for Part A.

- Overall summary of TEAE will include the number of patients with any TEAEs, drug-related TEAEs, ≥ Grade 3 TEAEs, treatment-emergent serious AEs (TESAEs), TEAEs leading to discontinuation (treatment and study);
- A summary of the number and percentage of patients reporting a TEAE by system organ class (SOC) and PT;

For Part B (MAD) only, the following AE summaries (as described in Section 7) will be provided:

- Overall summary of TEAE will include the number of patients with any TEAEs, drug-related TEAEs, ≥ Grade 3 TEAEs, treatment-emergent serious AEs (TESAEs), TEAEs leading to discontinuation (treatment and study);
- A summary of the number and percentage of patients reporting a TEAE by system organ class (SOC) and PT;
- A summary of the number and percentage of patients reporting a TEAE by severity, SOC and PT.
- A summary of the number and percentage of patients reporting a TEAE by causality, SOC and PT;
- A summary of the number and percentage of Maximum CTCAE recorded
- A summary of the number and percentage of patients reporting a Serious TEAE by system organ class (SOC) and PT;

AE summaries will be ordered in terms of decreasing frequency for SOC, and PT within SOC, in the Total group, and then alphabetically for SOC, and PT within SOC.

For each subject and each AE, the worst severity recorded will be attributed and used in the by-severity summaries. Similarly, the worst causality (most related to treatment) will be attributed and used in the by-causality summaries.

For Part A and Part B, by-subject listings of AEs will be presented by study part and treatment group for the following listings:

- All DLT events
- All TEAEs
- All SAEs
- All TESAEs
- TEAEs Leading to Study Discontinuation
- TEAEs Leading to Permanent Discontinuation of Study Drug
- TEAEs Leading to Death
- Non-TEAEs

The following information will be included in the listings: verbatim (reported term), PT, SOC, AE onset date (and time), AE end date (and time), AE duration, relationship to study drug, AE outcome, severity, and SAE indicator flag. Confirmed and suspected SARS-CoV-2 infections and/or COVID-19 cases will be recorded in the AE eCRF.

Pandemic related Impact of COVID-19 will be presented in listing, detailing the category of impact (example: Missed Visit, Missed Assessment, Early termination, Screen Failure, Adverse Event, Withdrawal of consent, Death, Replacement subject).

#### 8.8.2 Physical Examination

Physical exam results will be listed for Part A and B, sorted by study Part, subject ID, body system and date of exam.

## 8.8.3 Vital Signs

Vital signs (temperature, pulse rate, and diastolic and systolic blood pressure will be summarized (as described in Section 7) for observed values and change from baseline, at each visit measured.

#### 8.8.4 Clinical Laboratory Evaluation

For Part B only, clinical laboratory summary statistics (as described in Section 7) will be provided for serum chemistry, hematology, coagulation and urinalysis (specific gravity and pH only) for observed values and change from baseline by study visit.

A shift table will be provided to evaluate the change from baseline to each post-baseline visit in the lab value status (abnormal high, normal, abnormal low) for serum chemistry, hematology, and coagulation.

The following by-subject laboratory listings (values and change from baseline if applicable) will be provided by study part and treatment group using the enrolled patients and sorted by subject ID, laboratory evaluation and date measured:

- Serum Chemistry
- Hematology
- Coagulation
- Urinalysis
- Virus Serology (screening only)
- Serum and Urine Pregnancy test
- Lab abnormality  $\geq$  Grade 3 in Severity.

Toxicity, in reflection of safety laboratory results will be graded locally according to NCI-CTCAE v5.0 or higher and included in separate listings.

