## Key Exclusion Criteria

- 1. Diagnosis of primary progressive MS or secondary progressive MS
- 2. Uncontrolled or significant medical conditions (including active infection, chronic hepatitis, or Neuromyelitis Optica Spectrum Disorder) which, in the opinion of the Investigator, preclude participation
- 3. Has any of the following laboratory parameters at screening:
  - a. Hemoglobin < 10 g/dL
  - b. Platelet count  $< 100 \times 10^9/L$
  - c. White blood cell count outside the normal range and assessed as clinically significant by the Investigator
  - d. Alanine aminotransferase, aspartate aminotransferase, or alkaline phosphatase  $> 1.5 \times$  the upper limit of normal
  - e. Estimated glomerular filtration rate < 60 mL/min/1.73 m² based on the Cockcroft-Gault equation during screening
- 4. Positive for HIV, hepatitis B virus, or hepatitis C virus
- 5. Patients treated with glatiramer acetate, parenteral steroids or adrenocorticotropic hormone, β-interferon, or plasma exchange within the 3 months prior to first dose
- 6. Patients treated with sphingosine-1-phospate receptor modulators such as fingolimod, ozanimod, or siponimod within 6 months prior to first dose
- 7. Patients treated with cytotoxic agents (including, but not limited to, cladribine, mitoxantrone, cyclophosphamide, azathioprine, and methotrexate), laquinimod, teriflunomide, or IV gamma globulin within 12 months prior to first dose
- 8. Patients treated with monoclonal antibody therapy (including natalizumab, daclizumab, rituximab, ofatumumab, and ocrelizumab) within 24 months prior to first dose except anti-severe acute respiratory syndrome coronavirus 2 monoclonal antibodies
- 9. Patients previously treated with alemtuzumab, total lymphoid irradiation, mesenchymal stem cell or hematopoietic stem cell transplantation, or tolerance-inducing therapies for MS
- 10. Patients receiving any vaccination within 28 days prior to first dose
- 11. Patients with clinical signs and symptoms consistent with suspected COVID-19 or confirmed COVID-19 infection by appropriate laboratory test within the last 4 weeks prior to screening or on admission
  - Note: Patients who experienced symptoms consistent with COVID-19 or confirmed infection during the screening period (i.e., after signing the ICF but before dosing) may be rescreened after 4 weeks
- 12. Patients with a prior severe course of COVID-19 requiring extracorporeal membrane oxygenation (ECMO) or mechanical ventilation

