## 1.2. ANK-700

ANK-700 is a synthetic composed of a CNS-derived synthetic peptide, ANK-07, to enable liver-specific distribution and immune tolerance induction. The mechanism of action of ANK-700 harnesses natural tolerogenic pathways in the liver to re-educate pathogenic immune cells to become tolerant towards MS antigens. ANK-700 specifically targets the immune cells that drive MS and leaves the otherwise healthy components of the immune system intact to perform their natural, protective functions. Surrogates of ANK-700 have demonstrated efficacy in mouse models of MS. The mechanism by which ANK-700 induces immunologic tolerance is mediated by 3 mechanisms:

- Deletion of antigen-specific T cells
- Induction of anergy/clonal exhaustion of antigen-specific T cells
- Induction of regulatory T cells which control the antigen-specific T-cell response

Study ANK-700-01 in Relapsing-Remitting Multiple Sclerosis

Previous clinical research exploring the use of altered peptide ligands, derived from myelin peptides, to induce immunological tolerance in MS patients have observed an exacerbation of disease and/or an increase in inflammatory lesions (Bielekova 2000). However, subsequent studies using different peptide sequences and technologies to induce antigen-specific T-cell tolerance to myelin antigens have not shown these effects (Chataway 2018, Zubizarreta 2019).

Treatment for RRMS depends upon patient characteristics and comorbidities, the severity and activity of disease, and the safety profile of available therapies (Montalban 2018). Many current therapies suppress or modulate the immune system, but without the ability to target specific antigens. Many of the approved therapies for RRMS require vigilant monitoring against toxicities, including serious infections. There remains an unmet medical need for effective, targeted, well-tolerated therapies to treat RRMS.

For more information on the nonclinical findings, please see the ANK-700 Investigator's Brochure.

This first-in-human (FIH) study will be conducted in patients with RRMS with the aim of evaluating the tolerability of single and multiple intravenous (IV) administrations of ANK-700.

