# **5.2.** EXCLUSION CRITERIA

- 1. Diagnosis of PPMS or SPMS
- 2. Uncontrolled or significant medical conditions (including active infection, chronic hepatitis, or Neuromyelitis Optica Spectrum Disorder) which, in the opinion of the Investigator, preclude participation
- 3. Has any of the following laboratory parameters at screening:
  - a. Hemoglobin < 10 g/dL
  - b. Platelet count  $< 100 \times 10^9/L$
  - c. White blood cell count outside the normal range and assessed as clinically significant by the Investigator
  - d. Alanine aminotransferase (ALT), aspartate aminotransferase (AST), or alkaline phosphatase (ALP)  $> 1.5 \times$  the upper limit of normal
  - e. Estimated glomerular filtration rate < 60 mL/min/1.73 m² based on the Cockcroft-Gault equation during screening
- 4. Positive for HIV, hepatitis B virus (HBV), or hepatitis C virus (HCV)
- 5. Patients treated with glatiramer acetate, parenteral steroids or adrenocorticotropic hormone,  $\beta$ -interferon, or plasma exchange within the 3 months prior to first dose
- 6. Patients treated with sphingosine-1-phospate receptor modulators such as fingolimod, ozanimod, or siponimod within 6 months prior to first dose

Anokion US, Inc.

7. Patients treated with cytotoxic agents (including but not limited to cladribine, mitoxantrone, cyclophosphamide, azathioprine, and methotrexate), laquinimod,

teriflunomide, or IV gamma globulin within 12 months prior to first dose

- 8. Patients treated with monoclonal antibody (mAb) therapy (including natalizumab, daclizumab, rituximab, and ocrelizumab) within 24 months prior to first dose except antisevere acute respiratory syndrome coronavirus 2 monoclonal antibodies
- 9. Patients receiving any vaccination within 28 days prior to first dose
- 10. Patients previously treated with alemtuzumab, total lymphoid irradiation, mesenchymal stem cell or hematopoietic stem cell transplantation, or tolerance-inducing therapies for MS
- 11. Patients with clinical signs and symptoms consistent with suspected COVID-19 or confirmed COVID-19 infection by appropriate laboratory test within the last 4 weeks prior to screening or on admission
  - Note: Patients who experienced symptoms consistent with COVID-19 or confirmed infection during the screening period (i.e., after signing the ICF but before dosing) may be rescreened after 4 weeks
- 12. Patients with a prior severe course of COVID-19 requiring extracorporeal membrane oxygenation or mechanical ventilation

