# **6.1.9.** Clinical Laboratory Tests

The following laboratory parameters will be measured at screening and at the time points specified in the Schedule of Assessments (Table 1 and Table 2) and will be analyzed locally by a certified laboratory:

- A serum pregnancy test during screening for all women of childbearing potential (WCBP)
- Serum or urine pregnancy testing for all WCBP before each dose
- Hematology laboratory parameters include white blood cell (WBC) count, hemoglobin, hematocrit, platelet count, and WBC differential
- Blood chemistry laboratory parameters, including blood urea nitrogen, creatinine, glucose, AST, ALT, ALP, bilirubin (total and direct), electrolytes (sodium, chloride, bicarbonate, potassium), amylase, lipase, albumin, magnesium, calcium, and phosphorus
- Coagulation laboratory parameters, including prothrombin time, partial thromboplastin time or activated partial thromboplastin time, and international normalized ratio
- Complete urinalysis with qualitative analysis for protein (dipstick)
- HIV, HBV (hepatitis B surface antigen, hepatitis B core antibody, and hepatitis B surface antibody), and HCV testing (screening only)

Unscheduled assessments should be performed as clinically indicated.

For any out-of-range laboratory findings during screening, repeat laboratory testing may be performed at the discretion of the Investigator. Abnormal laboratory findings at screening should be recorded as medical history only if considered CS.

Clinical laboratory assessments should be performed before ANK-700/PBO infusion when applicable.

Study ANK-700-01 in Relapsing-Remitting Multiple Sclerosis

Laboratory findings assessed by the Investigator as CS, including but not limited to, those findings resulting in a drug interruption/hold/reduction/discontinuation or medical intervention, should be repeated to verify the out-of-range findings, followed to a satisfactory clinical resolution, and reported as an AE(s) (see Section 11.1.1 for definition of an AE).

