### 12.7. CLINICAL LABORATORY ASSESSMENTS

Presentation of laboratory values will be performed using International System units. All statistical summaries for laboratory values, including change from baseline, will be by dose/treatment group for Part B. Part A will be listed.

Abnormal laboratory findings will be also listed by number and percentage of patients with values  $\geq$  Grade 3 in severity.

A listing of individual patient hematology (including coagulation) and serum chemistry values outside the clinical reference ranges will be provided.

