## 8. STATISTICAL METHODS

All outputs will be produced using SAS® version 9.4 or a later version.

No hypothesis will be tested.

Summary statistics will be presented for all variables of interest for the ATAS population unless otherwise specified. Categorical variables will be summarized using numbers and percentages and be presented by dose level received. Continuous variables will be summarized by total number (n), mean, standard deviation (SD), median, and range (minimum and maximum). For log transformed data, the geometric mean will be provided along with the other summary statistics. Categorical data will be presented by frequency and percent of patients in the treatment group.

Listings will be sorted by Study Part, subject ID, Treatment, study visit, date and time, where applicable, unless otherwise specified.

Summary statistics for Part A and B will be presented in the following manner:

- For Part A, summary statistics will be provided for subject disposition with the following tables summarized:
  - o Disposition
  - Analysis populations
  - Demographics
  - Protocol Deviations
  - PK analysis
  - Summary of TEAE
  - o Summary of TEAE by System Organ Class and Preferred Term
- For Part B alone, summary statistics will be provided by treatment group, pooling the placebo group from each cohort for all tables.
- For Part A and B pooled, summary statistics will be provided by pooling the treatment groups with only the following tables summarized:
  - o Disposition
  - Analysis Populations
  - Demographics
  - o PK analysis

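### In Part B the only laboratory table that counts patients is a high/normal/low shift, so no table counts patients by severity of worsening per arm, and the protocol's Grade 3 or higher count has become a listing

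*SAP*

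**What the plan says.** **SAP 8.8.4** plans two kinds of laboratory table for Part B.

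- Descriptive statistics for chemistry, hematology, coagulation and two urinalysis items, "for observed values and change from baseline by study visit". SAP Section 8 sets the statistics: n, mean, SD, median, minimum and maximum.
- A shift table for chemistry, hematology and coagulation, to "evaluate the change from baseline to each post-baseline visit in the lab value status (abnormal high, normal, abnormal low". It has three states and no grading within a state.

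The other laboratory outputs in that section are by-subject listings. They include one of abnormalities of Grade 3 or higher, and separate listings of toxicity graded locally under CTCAE.

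**Protocol 12.7** asks for something more: "Abnormal laboratory findings will be also listed by number and percentage of patients with values" of Grade 3 or higher.

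**Protocol 5.2**, exclusion 3, removes patients for ALT, AST or ALP only when the screening value is above 1.5 x ULN. It also lets in a white cell count outside the normal range if the investigator does not judge it clinically significant.

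**Precedence.** Protocol Section 12 says the final SAP prevails where the two differ, and SAP Section 1 says the SAP replaces the protocol's statistical section. SAP Section 1 points to Section 10 for substantial differences, but Section 10 deals with missing data. SAP Section 12, on changes from the protocol, names none and defers them to the study report.

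**The concern.** A three-state shift table shows that a value crossed a limit of normal. It cannot show how far it went, and it cannot show worsening in a patient who starts beyond the limit. Here eligibility allows such patients for the liver enzymes, and Protocol 1.2 describes a molecule designed "to enable liver-specific distribution and immune tolerance induction". Safety is the primary objective, and SAP 3.1 gives a safety comparison of ANK-700 with placebo as the reason for the Part B sample size.

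The one planned output that would have counted patients by severity of a laboratory value, the protocol's Grade 3 or higher number and percentage, does not survive into the SAP. A reader comparing arms from the tables would therefore see how many patients crossed a limit of normal, but not how many worsened to a given severity. That reader would have to build the count from listings.

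**Working it through.** The plan states no figure to reproduce on this point: the study is descriptive and SAP 3.1 says no sample size calculation was done. The check applies the SAP's own rules to example patients.

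**Inputs from the documents**

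- Entry limit for ALT, AST and ALP: up to 1.5 x ULN (Protocol 5.2).
- Shift states: high, normal, low (SAP 8.8.4).
- Part B groups: 8 at 0.3 mg/kg, 8 at 1.0 mg/kg and 8 pooled placebo (SAP 3.1). Check: 2 cohorts x (8 + 4) = 24.

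**Assumed.** The fold rises of 3, 5 and 10, because the documents give none. A value is called high when it exceeds 1.0 x ULN.

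**Step 1. What the shift table records.** Final value = baseline x fold.

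| Baseline (x ULN) | 3-fold | 5-fold | 10-fold | Shift shown |
|---|---|---|---|---|
| 1.5 | 4.5 | 7.5 | 15 | high to high |
| 1.1 | 3.3 | 5.5 | 11 | high to high |

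A patient starting at 0.8 x ULN who reaches 1.1 x ULN and one who reaches 10 x ULN are both normal to high.

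**Step 2. What the summary statistics show.** Take one of 8 patients starting at 1.5 x ULN, with the other seven unchanged. The change is 1.5 x (fold - 1), and the mean change is that divided by 8.

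| Fold | Change in that patient (x ULN) | Mean | SD | Median | Maximum |
|---|---|---|---|---|---|
| 3 | 3.0 | 0.375 | 1.06 | 0 | 3.0 |
| 5 | 6.0 | 0.75 | 2.12 | 0 | 6.0 |
| 10 | 13.5 | 1.69 | 4.77 | 0 | 13.5 |

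The median does not move. The maximum exposes the value, but it does not say how many patients worsened or from what baseline.

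**Step 3. Protocol against SAP.** Protocol 12.7 says the findings are listed by number and percentage. The wording is loose, but a number and percentage of patients is a count, and a by-subject listing does not give one. Neither SAP Section 10 nor Section 12 mentions the difference.

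**Step 4. Whether the AE tables fill the gap.** SAP 8.8.1 tabulates Part B TEAEs by severity, Grade 3 or higher TEAEs and maximum CTCAE grade. A laboratory value enters these only if it was reported as an AE. Under Protocol 11.2.4 that depends on whether it led to a change in study drug or concomitant medication, or on the investigator's judgment. These tables overlap with a laboratory count but do not replace it.

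**Step 5. Size.** One patient in an arm of 8 is 1/8 = 12.5%.

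**The case against.** The strongest reply is that nothing is concealed. The by-visit maximum shows the extreme value for each arm. Individual values with change from baseline are listed by treatment group, and there is a dedicated listing of Grade 3 or higher abnormalities. With scheduled Part B safety samples after Day 1 only at D4, D7 and D22, plus early termination, counting patients out of 8 from a listing is easy. Clinically significant values become AEs and reach the AE tables, which carry the primary endpoint. A Grade 3 or higher AE in the monitoring window counts as a DLT, apart from the stated exclusion for intercurrent illness or other medication, and pauses the study. Patient protection during the trial therefore does not rest on this table. All of this stands, and it limits the point to reporting.

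It does not remove the point. Protocol 12.7 called for the count, and the SAP dropped it without a record.

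Four stronger readings are tempting and are not supported.

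- **That no table shows the severity of a laboratory change by arm.** The minimum and maximum of observed values and of change, by visit and treatment group, do show it. What is absent is a count of patients.
- **That unscheduled values are left out of the shift table.** Protocol 6.1.9 says "Unscheduled assessments should be performed as clinically indicated", and the SAP shifts to each post-baseline visit without saying whether unscheduled results count. It is silent, which is not an exclusion.
- **That the affected patients have the least hepatic reserve.** No section equates a value between 1.0 and 1.5 x ULN with reduced reserve, and Protocol 1.3 says patients with hepatic impairment are excluded.
- **That a probability of masked worsening can be given.** The documents state neither how many patients enter out of range nor how often such patients worsen.

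**Conclusion.** The point holds as a gap in the planned tables and an unrecorded departure from the protocol. In Part B, no table counts patients by severity of laboratory worsening by arm. The only laboratory table that counts patients treats any rise from an above-range baseline as no shift, and it merges small and large rises from a normal baseline. The Grade 3 or higher number and percentage in Protocol 12.7 has become a by-subject listing.

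The size is one patient, 12.5% of an arm of 8, for each such case. That a case occurs at all is an assumption, as are the fold rises used above. The entry limit applies at screening, and I find no definition of laboratory baseline in the SAP (screening or D1 pre-dose). The reasoning applies to any patient whose baseline value, however defined, is above range. The information can be recovered from the maxima and the listings, so this should be corrected because correction is cheap and serves the primary safety objective. It does not put the study's data at risk.

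**What to change.** In SAP 8.8.4:

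1. Restore the number and percentage of patients with Grade 3 or higher laboratory values, by 0.3 mg/kg, 1.0 mg/kg and pooled placebo.
2. Add a Part B table of baseline CTCAE grade against worst post-baseline grade per patient, by the same three groups. State that unscheduled values count, and state which value is baseline.
3. For ALT, AST, ALP and bilirubin, show each patient's maximum multiple of ULN by group.

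Only the first item restores something the protocol already promised. The other two are additions that close the gap in the shift table. If the sponsor prefers to keep listings only, the departure from Protocol 12.7 should be recorded in SAP Section 12 now, not left to the study report.

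The cost is SAP wording and one or two extra tables. SAP 8.8.4 already has laboratory toxicity graded, so no new data are needed.
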